# 8.2. Investigational Treatment

# 8.2.1. Dosing Schedule and Rationale

Subgam-VF is a 16% subcutaneous IgG product. The weekly dose of Subgam-VF administered will be calculated by taking the weekly equivalent of the subject's stable IGIV dose, multiplied by 1.37, a dose adjustment coefficient based on other licensed subcutaneous IgG products. If the subject was already receiving a weekly SCIG IgG there will be no dose adjustment. The Subgam-VF dose should remain the same throughout the study, if a subject's weight changes by >5% compared with baseline (screening) or the previous visit, the dose should be adjusted accordingly with the aim of maintaining a stable dose in terms of mg/kg. If the dosage needs to be increased to achieve the required trough IgG level, then this should first be discussed with the CRO Medical Monitor, who will, if needed, discuss with the Sponsor.

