# 13.6. Pharmacokinetic Analyses

The pharmacokinetics of Subgam-VF will be based on absolute and baseline-adjusted (trough adjusted at steady state) values and will be described using a non-compartmental method. Actual sample times rather than nominal times will be used to calculate pharmacokinetic parameters.

The following PK parameters will be calculated for the Subgam PK population: The maximum observed concentration ( $C_{max}$ ), the time at which  $C_{max}$  was apparent ( $t_{max}$ ), the area under the concentration versus time curve within a dosing interval ( $AUC_{0-\tau}$ ) and the systemic clearance (CL).

Pharmacokinetic variables will be summarized descriptively. This analysis will be conducted for subjects 2 to 5 years of age, 6 to 11 years of age, 12 to 15 years of age, all pediatric subjects (2 to 15 years of age), all adult subjects (aged 16 years and over), then for all subjects.

For the Gammaplex PK population,  $sAUC_{0-\tau}$  will be calculated as the area under the concentration versus time curve within a dosing interval (21 or 28 days), standardized to one week i.e.  $AUC_{0-\tau}$  (21 day)/3 or  $AUC_{0-\tau}$  (28 day)/4. For the Subgam PK population,  $sAUC_{0-\tau}$  is equivalent to  $AUC_{0-\tau}$  (i.e. no standardization required as dosing is weekly).

All PK data collected on all subjects in the Subgam PK population will be listed. The PK population i.e. Subgam PK population combined with the Gammaplex PK population (historical data following administration of Gammaplex 5% IGIV) will be used for the primary and secondary statistical PK analyses.

The trough levels of total IgG will be summarized descriptively for all the subjects in the ITT population. Trough levels in the ITT population will be compared with those from the Gammaplex PK population.

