## 13.6.1. Primary Statistical Analysis

Data will be pooled with historical data and a treatment variable defined (Subgam-VF or Gammaplex IGIV). Log transformed  $sAUC_{(0-\tau)}$ , ( $AUC_{(0-\tau)}$  standardized to one week) will be analyzed using a mixed model fitted including treatment, and allowing for variability to be different between treatment groups. The mean difference (Subgam-VF or Gammaplex IGIV) between treatments with 90% Confidence Interval (CI) will be back transformed to give an estimate of the ratio (Subgam-VF/ Gammaplex IGIV) of  $sAUC_{(0-\tau)}$ . If the resulting 90% CI for the ratio lies within the equivalence limit of (0.80, 1.25), it will be concluded that there is equivalence in  $sAUC_{(0-\tau)}$  and thus the dosing factor of 1.37 for Subgam-VF (in addition to the adjustment for dosing interval) gives equivalent exposure at steady state to Gammaplex IGIV.

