# 13.6.2. Secondary Statistical Analyses

- i. The primary analysis method will be repeated with data derived from baseline-adjusted concentrations.
- ii. A term for dosing interval within treatment will be included in the model described in the primary analysis so that ratios with 90% CI can be presented for Subgam-VF relative to both the 21 day and 28 day dosing interval regimens of Gammaplex.
- iii. The primary analysis model will be extended to include any significant (at the 10% level) covariates or covariate by treatment interactions. Covariates considered for inclusion will include age category, weight, BMI and sex.
- iv. The effect of previous treatment (SCIG or IGIV) on  $AUC_{(0-\tau)}$  in the Subgam PK population will be analysed. If the resulting 90% CI for the ratio lies within the equivalence limit of (0.80, 1.25), it will be concluded that the previous treatment does not affect exposure at steady state. If this is the case then the refined dose adjustment with 90% CI will be presented on the full PK population (in addition to on the PK Dose Adjustment population described below).
- v. In addition, the data from the current study will be restricted to a PK Dose Adjustment population and analysed as per the primary analysis. A refined dose adjustment will be estimated as 1.37/the ratio (Subgam-VF / Gammaplex IGIV) of geometric means for sAUC(0- $\tau$ ) and presented with 90% CI.

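### The factor 1.37 is judged on, and may be re-estimated from, a population that includes prior-SCIG subjects to whom it was never applied, and item v uses its nominal rather than its delivered value

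*Protocol*

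**What the plan says.** **Dosing.** Protocol 7 and 8.2.1 give prior-IGIV subjects 1.37 times their weekly-equivalent IGIV dose. For the others: "If the subject was already receiving a weekly SCIG IgG there will be no dose adjustment". Section 8.2.1 wants the mg/kg dose kept stable but provides for a rise: "If the dosage needs to be increased to achieve the required trough IgG level", after discussion with the medical monitor.

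**Primary analysis (13.6, 13.6.1).** Gammaplex AUC is divided by 3 or 4 according to dosing interval. For Subgam-VF there is "no standardization required as dosing is weekly". The model contains treatment only and uses the full PK population, prior-SCIG subjects included. If the 90% CI lies within 0.80-1.25, the protocol concludes that "thus the dosing factor of 1.37 for Subgam-VF (in addition to the adjustment for dosing interval) gives equivalent exposure at steady state" to Gammaplex.

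**Secondary analyses (13.6.2).**
- Item iii: "Covariates considered for inclusion will include age category, weight, BMI and sex". Dose is not named, though the list is not closed.
- Item iv compares AUC by prior route within Subgam-VF subjects. If that 90% CI lies within 0.80-1.25: "If this is the case then the refined dose adjustment with 90% CI will be presented on the full PK population", in addition to the item v estimate.
- Item v uses the PK Dose-Adjustment population (13.2.2.3), which leaves out prior-SCIG subjects: "A refined dose adjustment will be estimated as 1.37/the ratio (Subgam-VF / Gammaplex IGIV) of geometric means for" weekly-standardised AUC.

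**Dose and clearance.** SAP 13.1 summarises mg/kg dose in SCIG03 only. Against the historical studies, 13.6 plans a trough comparison: "Trough levels in the ITT population will be compared with those from the Gammaplex PK population". Clearance (CL) is listed for the PK population in the synopsis and in 11.1, but for the Subgam PK population in 13.6. The SAP (sections 3 and 14) leaves PK analysis to a PK Analysis Plan that is not among the documents.

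**The concern.** Refining the coefficient is a secondary objective (Protocol 5.2). The numerator 1.37 has meaning only for subjects whose weekly dose was 1.37 times a known IGIV dose. The protocol accepts this by defining a population without prior-SCIG subjects. Item iv then allows them back, and 13.6.1 never takes them out before it concludes on the factor.

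The item iv criterion tests a different thing. It asks whether AUC is similar by prior route. A prior-SCIG subject may be on a dose that reflects some other conversion, or none; the documents do not give it. Even with identical exposure, these subjects would narrow the CI of a coefficient on which they carry no direct information.

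Two further assumptions sit behind item v. The delivered multiplier must still be 1.37 at PK sampling. And IGIV-equivalent weekly mg/kg dose relative to clearance must have been similar in SCIG03 and in GMX01/GMX04. The only safeguard stated for the latter is similar eligibility criteria (Protocol 7). A dose difference not matched by clearance would be read as a property of the subcutaneous route, and the 90% CI would not reflect it.

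**Working it through.** **Inputs.** Log-SD 0.181, 30 evaluable Subgam-VF subjects, limits 0.80-1.25 and 90% CI are from Protocol 13.1 and 13.6.1. The number of historical subjects, the share of prior-SCIG subjects, the exposure difference by prior route and the frequency of dose increases are not given. They are assumed below, so the results are sensitivity ranges.

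**The plan's own figure.** With 30 historical subjects, power is 99.8% at a ratio of 1.00 and 85.5% at 1.10. That agrees with the stated figures (above 98%, and 86%), so 30 vs 30 is used. At 0.90 it gives 80%.

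**When 1.37/ratio is right.** With AUC = F x dose / CL and true coefficient c, ratio = (1/c) x (dose ratio / clearance ratio). So 1.37/ratio = c exactly when dose ratio / clearance ratio = 1.37. Scatter of individual multipliers around a geometric mean of 1.37 does no harm.

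**Item iv.** Let theta be the prior-SCIG/prior-IGIV exposure ratio and p the prior-SCIG share. Then full-population coefficient = item v coefficient / theta^p. The criterion passes when theta lies between 0.80 x exp(t x SE) and 1.25 x exp(-t x SE), with SE = 0.181 x sqrt(1/n1 + 1/n2) and t = 1.701 (28 df).

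| Prior-IGIV / prior-SCIG | SE | theta that passes | Coefficient if item v gives 1.37 |
|---|---|---|---|
| 20 / 10 | 0.0701 | 0.901-1.109 | 1.37/1.109^(1/3) = 1.32 to 1.37/0.901^(1/3) = 1.42 |
| 15 / 15 | 0.0661 | 0.895-1.117 | 1.37/1.117^(1/2) = 1.30 to 1.37/0.895^(1/2) = 1.45 |

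These are the edges. By simulation (Welch CI), a true 10% difference by prior route passes in about 54% (20/10) or 59% (15/15) of studies. The mean shift among those that pass is about 1.6% or 2.7%.

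**Section 13.6.1.** Put the like-for-like ratio in prior-IGIV subjects at 0.80, the limit, so that equivalence should be declared in 5% of studies. Let 10 of the 30 subjects be prior-SCIG:
- with 10% higher exposure, the pooled ratio is 0.80 x 1.10^(1/3) = 0.826, and equivalence is declared in about 16%;
- with 20% higher exposure, it is 0.80 x 1.20^(1/3) = 0.850, and equivalence is declared in about 32%.

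**Item v with raised doses.** If 20% of subjects are raised by 20%, the delivered geometric mean multiplier is 1.37 x 1.20^0.2 = 1.42. With true coefficient 1.37 and proportional exposure, the ratio is 1.20^0.2 = 1.037. The nominal formula reports 1.37/1.037 = 1.32. With the delivered multiplier it is 1.42/1.037 = 1.37.

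**The case against.** The other side has real points.

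- **Item iv is conditional and additional.** The item v estimate is always shown. A mean shift of 1.6% (20/10) is small against a 90% CI factor of about 1.08 (30 vs 30). This stands, and it limits the size of the point. It does not make the extra estimate informative about 1.37.
- **Prior-SCIG subjects may already be on a converted dose.** Reading a month as one infusion interval, 300-800 mg/kg/month x 1.37 is 103-274 mg/kg/week at 28 days (137-365 at 21 days), close to the SCIG entry range of 110-300. A reader might infer that these subjects were on systematically different doses. The documents do not show that. Nor do they show that the conversion was 1.37.
- **Clearance is planned, and the PK Analysis Plan is unseen.** CL relates dose to AUC, so it would be wrong to say that dose is ignored. But CL does not enter 1.37/ratio, and the sections differ on whether it covers Gammaplex subjects. The PK Analysis Plan could add a dose comparison, so the gap is one in the documents seen.
- **Dose increases may be rare.** Section 8.2.1 asks for a stable dose. The 20% raised by 20% is an illustration, not a forecast.

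A reader might also infer that a dose covariate or dose-normalised AUC should be required. The documents do not support that. Dose may be confounded with clearance, and then adjustment can move the coefficient away from the truth.

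**Conclusion.** The concern holds for the inference about 1.37. Section 13.6.1 and item iv attach the factor to subjects who did not receive it, and item v uses its nominal value whatever was delivered. Under the assumed mixes, item iv can move the coefficient from 1.37 to anywhere in 1.32-1.42 or 1.30-1.45, with typical shifts of 1.6% to 2.7% at a true 10% difference. The 13.6.1 conclusion can be reached in 16% to 32% of studies instead of 5%. Raised doses can turn 1.37 into 1.32.

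Two stronger readings are not supported. The first is that the primary equivalence test is invalid: the primary objective (5.1) compares AUC between regimens as given, and the test answers that. The second is that SCIG03 and the Gammaplex studies differed in dose: no imbalance is documented, and the documents give no historical doses. The direction and size of any actual bias cannot be determined from them.

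**What to change.** Keep the primary model, population and equivalence test for AUC.

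1. In 13.6.1, limit the conclusion to equivalence of weekly-standardised AUC between regimens as given. Draw the inference about 1.37 from the PK Dose-Adjustment analysis already planned in item v.
2. In item iv, keep the comparison by prior route and drop the full-population coefficient.
3. In item v, replace the nominal 1.37 by the geometric mean of actual weekly Subgam-VF mg/kg dose at PK sampling over pre-study weekly IGIV mg/kg dose. Take the 90% CI from log(sAUC / own multiplier). List subjects whose mg/kg dose was raised, but do not exclude them, because that selects on exposure.
4. Tabulate weekly-equivalent mg/kg dose by study and, within SCIG03, by prior route, with CL alongside. Reconcile the synopsis and 11.1 with 13.6 on whether CL covers Gammaplex subjects.

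Dose-covariate or dose-normalised models are optional sensitivity analyses only. No change to dosing is implied.

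**Cost.** Wording and a few tables. Prior dose and interval are recorded (Protocol 7.12) and actual mg/kg dose is calculated at each infusion (SAP 13.1). Historical doses must be retrieved, and are assumed available because the AUCs are. The main price is power for the 1.37 inference:

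| Subjects | Ratio 1.00 | Ratio 1.10 | Ratio 0.90 |
|---|---|---|---|
| 30 vs 30 (all) | 99.8% | 85.5% | 80% |
| 20 vs 30 | 99% | 78% | 72% |
| 15 vs 30 | 97% | 70% | 64% |

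Power of the primary AUC test is unchanged. Own multipliers widen the 90% CI factor in item v from 1.092 to about 1.096 (20 vs 30, 20% raised by 20%).

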## 13.6.3. Exploratory Analysis

PK modelling will be performed to explore alternative dosing schedules. For example; PK modelling and simulation will be carried out to compare weekly administration to a biweekly schedule at double the weekly dose and assess IgG exposure.

Full details of the PK and associated statistical methods will be described in a PK Analysis Plan.

## 14. PROVISION OF ADDITIONAL INFORMATION

On request, the Investigator will supply the Sponsor with additional data relating to the study, or copies of relevant source records. In case of particular issues or governmental queries, it is also necessary to have access to the complete study records, provided that the subject's confidentiality is protected in accordance with applicable regulations.

## APPENDIX I: ADVERSE EVENT DEFINITIONS AND REPORTING

Adverse Event

#### **ABBREVIATIONS**

BPL	Bio Products Laboratory Limited
CRF	Case Report Form
CRO	Contract Research Organization
ECG	Electrocardiogram
eCRF	Electronic Case Report Form
FDA	US Food and Drug Administration
ICF	Informed Consent Form
IEC	Independent Ethics Committee
IMP/IP	Investigational Medicinal Product/Investigational Product
IRB	Institutional Review Board
SAE	Serious Adverse Event
SmPC	Summary of Product Characteristics

#### **Definitions of Adverse Events** 1.

#### **Adverse Events** 1.1

Definition: Adverse event means any untoward medical occurrence associated with the use of a drug in humans, whether or not considered drug related.

Suspected Unexpected Serious Adverse Reaction

An adverse event (also referred to as an adverse experience) can be any unfavorable and unintended sign (e.g. an abnormal laboratory finding), symptom, or disease temporally associated with the use of a drug, and does not imply any judgment about causality. An adverse event can arise with any use of the drug (e.g., off-label use, use in combination with another drug) and with any route of administration, formulation, or dose, including an overdose.

All AEs, whether or not considered by the Investigator to be related to the IMP (test product, comparator or placebo), must be described and recorded on the appropriate Adverse Event forms in the case report form (CRF)/electronic case report form (eCRF). Where possible, a diagnosis should be made. Anticipated fluctuations of preexisting conditions, including the disease under study, that do not represent a clinically significant exacerbation or worsening need not be considered AEs.

# Infusion-Related Adverse Events

All AEs that occur from the start of the infusion until 72 hours from the end of the infusion will be recorded as temporally related to the infusion.

Page 49 of 87

# Clinical Laboratory and Other Adverse Events

A laboratory result that is considered by the Investigator to be clinically significant or have a clinically significant pathological change from baseline should be recorded as an AE.

Other abnormal results (e.g. x-rays, scans, physical examination findings) that worsen from baseline and/or are considered clinically significant should also be recorded as AEs. The Investigator will exercise his or her medical and scientific judgment in deciding whether an abnormal laboratory finding or other abnormal assessment is clinically significant.

## Reporting

Adverse events should be reported and documented in accordance with the procedures outlined in this section. All AEs occurring during the study must be documented on the relevant CRF/eCRF pages. The following data should be documented for each AE:

- Description of the symptom event
- Classification of "serious" or "not serious"
- Severity
- Date of first occurrence and date of resolution (if applicable)
- Action taken
- Causal relationship
- Outcome of event (unknown, recovered, not yet recovered, recovered with sequelae, death [with date and cause reported])

## Pregnancy

Subjects will be instructed that a known or suspected pregnancy occurring during the study should be reported to the Investigator. The Investigator should also be notified of a pregnancy occurring during the study but confirmed after completion of the study. If a subject is found to be pregnant after inclusion in the study, the subject must be withdrawn from the study. Any pregnancy will be followed to term and the status of mother and child will be reported to the Sponsor after delivery.

Full details of any pregnancy will be recorded on the AE page of the CRF/eCRF, and a Pregnancy Report Form will be completed. A copy of the Pregnancy Report Form must be faxed to the CRO within 24 hours.

At the end of the study, it is expected that subjects will continue treatment with other immunoglobulin products. Any adverse events which occur after last study visit are more likely related to the continued treatment with non-study immunoglobulin products and therefore extended use of contraception and follow-up of pregnancies occurring after end of study visit are not appropriate in this study. Subjects of child bearing potential should

be advised of the risks of pregnancy in accordance with the relevant product information for their ongoing therapy.

# 1.2 Suspected Adverse Reaction

Definition: Suspected adverse reaction means any adverse event for which there is a reasonable possibility that the drug caused the adverse event. For the purposes of IND safety reporting, 'reasonable possibility' means there is evidence to suggest a causal relationship between the drug and the adverse event. A suspecte d adverse reaction implies a lesser degree of certainty about causality than adverse reaction, which means any adverse event caused by a drug.

The following are examples of types of evidence that would suggest a causal relationship between the drug and the adverse event to determine *Reasonable possibility*.

- A single occurrence of an event that is uncommon and known to be strongly associated with drug exposure (e.g., angioedema, hepatic injury, Stevens-Johnson Syndrome)
- One or more occurrences of an event that is not commonly associated with drug exposure, but is otherwise uncommon in the population exposed to the drug (e.g. tendon rupture)
- An aggregate analysis of specific events observed in a clinical trial (such as known consequences of the underlying disease or condition under investigation or other events that commonly occur in the study population independent of drug therapy) that indicates those events occur more frequently in the drug treatment group than in a concurrent or historical control group

Suspected adverse reactions are the subset of all adverse events for which there is a reasonable possibility that the drug caused the event. Inherent in this definition, and in the requirement to report suspected adverse reactions, is the need for the Sponsor to evaluate the available evidence and make a judgment about the likelihood that the drug actually caused the adverse event.

#### 1.3 Adverse Reaction

Definition: An adverse reaction means any adverse event caused by a drug. Adverse reactions are a subset of all suspected adverse reactions where there is reason to conclude that the drug caused the event.

## 1.4 Serious Adverse Event or Suspected Adverse Reaction

Definition: An adverse event or suspected adverse reaction is considered "serious" if, in the view of either the investigator or Sponsor, it results in any of the following outcomes:

Page 51 of 87

- Death,
- A life-threatening adverse event, [See Section 1.5]
- Inpatient hospitalization or prolongation of existing hospitalization,
- A persistent or significant incapacity or substantial disruption of the ability to conduct normal life functions,
- A congenital anomaly/birth defect.
- Important medical events that may not result in death, be life-threatening, or require hospitalization may be considered serious when, based upon appropriate medical judgment, they may jeopardize the patient or subject and may require medical or surgical intervention to prevent one of the outcomes listed in this definition. Examples of such medical events include allergic bronchospasm requiring intensive treatment in an emergency room or at home, blood dyscrasias or convulsions that do not result in inpatient hospitalization, or the development of drug dependency or drug abuse.

Hospitalization does not include hospitalizations for elective procedures for pre-existing conditions that did not worsen from baseline)

If either the Sponsor or investigator believes that the event is serious, the event must be considered serious and evaluated by the Sponsor for expedited reporting.

The following events of special interest will always be regarded as serious::

- Anaphylaxis or anaphylactoid reaction
- Myocardial infarction
- Stroke
- Pulmonary embolism
- Any thromboembolic event (TEE)
- Laboratory documented infection with blood borne virus
- Acute renal failure
- Any transmissible spongiform encephalopathy

In general, information that might materially affect the risk-benefit assessment of a medicinal product or that would suggest changes in the way it is to be administered or to the way a clinical investigation should be conducted should be reported in an expedited manner. Examples include the following:

- Single case reports of an expected adverse reaction with an unexpected outcome (e.g. fatal outcome)
- For an expected serious adverse reaction, an increase in the rate of occurrence that is judged to be clinically important
- A significant hazard to the patient population, such as lack of efficacy in treating life-threatening diseases or an event which is significant enough to lead to

important changes in the way a medicine is developed (e.g. change in dose, monitoring, consent forms).

- A major new safety finding from a newly completed animal study
- An SAE associated with a study procedure that could modify the conduct of the trial

